7.1.2. Solicited Reactogenicity Events

The occurrence of local and systemic reactogenicity symptoms will be assessed similarly to unsolicited AEs, with the number and proportion of participants experiencing each safety event at any point during the reactogenicity period (first 7 days after vaccination), along with the associated exact 95% CI. Collapsed comparisons will be made as in Section 7.1.1 as well.

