In light of the highly favorable data from non-clinical studies, ALFQ moved into human clinical trials in separate studies involving candidate malaria and COVID-19 vaccines. In the malaria vaccine trials, the ALFQ adjuvant was administered with the FMP013 (NCT04268420) and FMP014 (NCT04296279) formulations in low (20 µg protein antigen, 100 µg 3D-PHAD®, 50 µg QS-21) and high doses (40 µg protein antigen, 200 µg 3D-PHAD®, 100 µg QS-21). In the COVID-19 vaccine trial (NCT04784767), the ALFQ adjuvant was administered with a spike-ferritin nanoparticle (SpFN) antigen at consistent dosages in both the low SpFN dose (25 µg SpFN antigen, 200 µg 3D-PHAD®, 100 µg QS-21) and high SpFN dose (50 µg SpFN antigen, 200 µg 3D-PHAD®, 100 µg QS-21) groups. Except for the vaccinations in Part B of FMP014, vaccinations in these studies have been completed and post-vaccination safety data is available. In summary, ALFQ local reactogenicity in these studies appears to be comprised primarily of local pain and tenderness that is omnipresent, mild to moderate, and short-lived across both products and doses. Systemic reactogenicity was mostly mild to moderate with the most commonly reported symptoms consisting of headache, fever, chills, fatigue, and myalgia. In addition, there was one case of severe fatigue in FMP013 that occurred 24 hours post-injection and lasted less than 6 hours and one case of severe flu-like symptoms (severe fever chills, myalgias, and moderate temperature) in a FMP014 high dose participant that lasted less than 24 hours. No SAEs were reported in the FMP014 and EID030 trials; however, there were two SAEs reported in FMP013, Grade 3 right ankle hemarthrosis and Grade 4 acute appendicitis, both of which were assessed by the investigator as not related to the investigational products. No deaths or related SAEs were reported in these studies.

Safety data from this study, the malaria vaccine studies, and the SpFN + ALFQ vaccine (Joyce, 2021) study will contribute to the ALFQ safety profile, which will support its use with future experimental vaccine candidates.

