12.2.3. Safety Analysis

AEs will be listed individually and summarized by body system and preferred terms within a body system for each treatment group. Serious and/or unexpected AEs will also be discussed on a case-by-case basis. For the tabulation of the AEs by body system, a participant will be counted only once in a given body system. For example, a participant reporting nausea and diarrhea will be reported as one participant, but the symptoms will be listed as 2 separate AEs within the class. Therefore, the total number of AEs reported within a body system may exceed the number of participants within the body system reporting AEs. AEs will also be described by time period (i.e., overall and within 28 days of vaccination).

The occurrence of local and systemic reactogenicity symptoms, AEs and SAEs will be assessed as the proportions of participants experiencing such safety events along with 95% CIs. A key comparison of interest is between participants receiving vaccination with and without ALFQ (i.e., Groups 1+2 vs. Groups 3+4). Between group and collapsed comparisons will be performed using a chi-square (or exact test as appropriate).

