4. INVESTIGATIONAL PLAN

4.1. Overall Study Design and Plan

This is a Phase I randomized, double-blind, placebo-controlled clinical trial to define the safety and immunogenicity of IHV01/A244 with and without ALFQ at a full dose and at a fractional dose in a late boost setting for participants who had previously received the AIDSVAX®B/E with or without ALVAC in RV306. Participants will be randomized to receive 2 intramuscular (IM) injections, either IHV01/A244 (target of n=64 total, with n=16 per study arm) or saline placebo (target of n=16 total, with n=4 per study arm), into the same quadriceps muscle at Day 0. Half of the IHV01/A244 recipients will receive the full IHV01 (FLSC) dose (Groups 1 and 3) while the other half (Groups 2 and 4) will receive a fractional dose of each vaccine, which is one fifth of the standard dose. Groups 3 and 4 will also receive ALFQ. Enrollment will be sequential, with Groups 1 and 2 accruing first with a 2:2:1 ratio of full dose to fractional dose to placebo, followed by enrollment into Groups 3 and 4 with the same targeted allocation ratios. After the first 8 participants are enrolled across Groups 1 and 2, the Safety Monitoring Committee (SMC) will review 7 days of safety data from these participants to determine whether enrollment can continue. Enrollment into Groups 1 and 2 will continue unrestricted after any safety concerns raised by the SMC are addressed and the Sponsor gives their approval for the continuation of enrollment. Enrollment into Groups 3 and 4 will commence after enrollment into Groups 1 and 2 has been completed, the SMC has reviewed 7 days of safety data from all Group 1 and Group 2 participants, and the Sponsor gives their approval. Enrollment into Groups 3 and 4 will follow a similar approach with an SMC review of 7 days of safety data from the first 8 participants enrolled across both groups, and Sponsor approval before enrollment can continue unrestricted in Groups 3 and 4.

Participants will receive 2 IM injections, either IHV01/A244 (n=64) or saline placebo (n=16) at Day 0, and return for follow up at 1, 7, 14, 168, and 336 days after vaccination (protocol version 5.0, section 7.2). Figure 1 gives a schematic of the study design, with the RV306 groups shown on the left and the RV546 groups on the right.

Figure 1: Study Schematic

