5.8. Multiple Comparisons/Multiplicity

For comparisons of safety outcomes, 5%-level two-sided tests will be made. Some of these may be implicit comparisons based on the overlap of group-level confidence intervals (i.e. non-overlapping 95% CIs mean rejecting the null hypothesis of no difference between groups at the 0.05-level).

To compare primary immunogenicity outcomes (antigen-specific plasma IgG binding responses, as measured by log AUC over time) across all groups, 5%-level two-sided tests will be used. When differences are found, pairwise comparisons between vaccination groups will be made using the Bonferroni-Holm step-down procedure [1] and a 5% significance threshold for the adjusted p-values; if no difference is found across all groups, no pairwise comparisons will be made. Collapsed comparisons will be considered separately and will be made with 2.5%-level two-sided tests, even when no pairwise differences are observed.

Further exploratory comparisons for immunogenicity endpoints across all groups will be adjusted for multiplicity by a Bonferroni adjustment: multiplying p-values by the number of assays in the same set (e.g. across antigens for a given antibody test; see Section 3.2.2 for sets of assays). Then a similar process as above will be followed, with pairwise comparisons following a significant overall test and Bonferroni-Holm step-down procedure (with a 5% significance level) to account for the multiple pairwise tests.

These adjustments are intended to improve control of the type-I error across comparisons for the same outcome measure and time point (e.g. Geometric Mean Titers (GMTs) for gp120A244 plasma IgG binding at Day 14) rather than across outcome measures and/or time. This level of type-I error control will still allow for exploratory findings that would be assessed further in future studies.

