7.1. Primary Safety Analysis

7.1.1. Unsolicited Adverse Events

Unsolicited AEs will be listed and summarized by MedDRA system order class (SOC) and preferred term (PT) for each vaccination group. These will be described overall and within 28 days post-vaccination. A participant will be counted only once per PT per reporting period. SAEs, unexpected AEs, and AESIs will be summarized and listed. The number and percentage of participants reporting each PT, along with the associated 95% exact Clopper-Pearson CI for the underlying probability of the event, will be presented.

The likelihood of reporting AEs, SAEs, and AESIs will be compared between collapsed groups (Groups 1+2 vs. Groups 3+4 to assess ALFQ safety, Groups 1+3 vs. Groups 2+4 to assess vaccine dose) via exact binomial tests. If computational challenges arise, Chi-squared tests may be used instead. Calculated confidence intervals will be used to compare pairs of individual vaccination groups, instead of formal hypothesis testing; when CIs for the same event in two groups do not overlap, this corresponds to a p-value of less than 0.05 for the analogous exact binomial test.

Unsolicited AEs will also be tabulated by investigator-determined relationship to investigational product and severity for each vaccination group.

Incident HIV infections, as diagnosed by the algorithm in Section 11.1.4.4 of the protocol, will be presented in a listing.

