^b See listing of Serious Adverse Events												

Table 14: Adverse Events Occurring in 5% of Participants in Any Vaccination Group by MedDRA System Organ Class and Preferred Term, and Vaccination Group

MedDRA System Organ Class	MedDRA Preferred Term	Full IHV01/A244 (N=X)			Fractional IHV01/A244 (N=X)			Full IHV01/A244 + ALFQ (N=X)			Fractional IHV01/A244 + ALFQ (N=X)			Placebo (N=X)			All Participants (N=X)		
		n	%	Events	n	%	Events	n	%	Events	n	%	Events	n	%	Events	n	%	Events
Serious Adverse Events																			
All	All	x	x.x	x	x	x.x	x	x	x.x	x	x	x.x	x	x	x.x	x	x	x.x	x
SOC1	PT1	x	x.x	x	x	x.x	x	x	x.x	x	x	x.x	x	x	x.x	x	x	x.x	x
Etc.	Etc.																		
Other (Non-Serious) Adverse Events																			
All	All	x	x.x	x	x	x.x	x	x	x.x	x	x	x.x	x	x	x.x	x	x	x.x	x
SOC1	PT1	x	x.x	x	x	x.x	x	x	x.x	x	x	x.x	x	x	x.x	x	x	x.x	x
Etc	Etc																		
Solicited Adverse Events																			
All	All	x	x.x	x	x	x.x	x	x	x.x	x	x	x.x	x	x	x.x	x	x	x.x	x
SOC1	PT1	x	x.x	x	x	x.x	x	x	x.x	x	x	x.x	x	x	x.x	x	x	x.x	x
Etc	Etc																		
Clinical Laboratory Adverse Events																			
All	All	x	x.x	x	x	x.x	x	x	x.x	x	x	x.x	x	x	x.x	x	x	x.x	x
SOC1	PT1	x	x.x	x	x	x.x	x	x	x.x	x	x	x.x	x	x	x.x	x	x	x.x	x
Etc	Etc																		
Note: N = Number of participants in the Safety Population; n = Number of participants reporting event; Events = Total frequency of events reported.																			

Table 15: Collapsed Comparisons of the Proportion of Participants Experiencing Adverse Events by Event Type

Event Type	Full IHV01/A244 (N=X)	Fractional IHV01/A244 (N=X)	p-value ^a	Any ALFQ (N=X)	No ALFQ (N=X)	p-value ^a
	n (%)	n (%)		n (%)	n (%)	
Solicited Adverse Events						
Any Solicited Symptom	x (x.x)	x (x.x)	0.xx	x (x.x)	x (x.x)	0.xx
Moderate (Grade 2) ^b	x (x.x)	x (x.x)	0.xx	x (x.x)	x (x.x)	0.xx
Severe (Grade 3) ^b	x (x.x)	x (x.x)	0.xx	x (x.x)	x (x.x)	0.xx
Any Systemic Symptom	x (x.x)	x (x.x)	0.xx	x (x.x)	x (x.x)	0.xx
Moderate (Grade 2) ^b	x (x.x)	x (x.x)	0.xx	x (x.x)	x (x.x)	0.xx
Severe (Grade 3) ^b	x (x.x)	x (x.x)	0.xx	x (x.x)	x (x.x)	0.xx
Any Local Symptom	x (x.x)	x (x.x)	0.xx	x (x.x)	x (x.x)	0.xx
Moderate (Grade 2) ^b	x (x.x)	x (x.x)	0.xx	x (x.x)	x (x.x)	0.xx
Severe (Grade 3) ^b	x (x.x)	x (x.x)	0.xx	x (x.x)	x (x.x)	0.xx
Unsolicited Adverse Events						
Any Serious Adverse Event	x (x.x)	x (x.x)	0.xx	x (x.x)	x (x.x)	0.xx
Any Adverse Event of Special Interest	x (x.x)	x (x.x)	0.xx	x (x.x)	x (x.x)	0.xx

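### The full versus fractional dose test for solicited events ignores the ALFQ stage and loses power where local reactions are near universal with ALFQ

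*SAP*

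**What the plan says.** SAP 7.1.1 specifies the dose comparison for adverse events as "Groups 1+3 vs. Groups 2+4 to assess vaccine dose) via exact binomial tests". Its fallback is also unstratified: "If computational challenges arise, Chi-squared tests may be used instead". SAP 7.1.2 carries this over to solicited events: "Collapsed comparisons will be made as in Section 7.1.1 as well". SAP 5.8 sets the level: "For comparisons of safety outcomes, 5%-level two-sided tests will be made". In SAP Appendix 1, Table 15 gives a dose p-value for each solicited row, including "Any Local Symptom". Protocol 12.2.3 does not stratify either: "Between group and collapsed comparisons will be performed using a chi-square (or exact test as appropriate".

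On design, SAP 4.1 plans active vaccine with a "target of n=64 total, with n=16 per study arm". Groups 1 and 2 accrue first at 2:2:1 (full, fractional, placebo), then Groups 3 and 4 at the same targeted ratios. SAP 4.2 calls the design factorial.

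On expected rates, Protocol 5.5.3 describes ALFQ reactogenicity in earlier malaria and COVID-19 vaccine trials as mainly "local pain and tenderness that is omnipresent". It says nothing comparable about systemic symptoms or the other local signs.

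**The concern.** Dose is randomised separately without ALFQ and with ALFQ, but the planned test merges the two stages. If nearly everyone given ALFQ has a local reaction, half of each dose arm carries almost no information about dose. The gap between the stages is then counted as random variation in the pooled 2×2 table. The test becomes stricter than its nominal level, and a dose difference that shows only without ALFQ is harder to detect.

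Solicited reactions are primary safety endpoints (SAP 3.2.1). A non-significant dose p-value in Table 15 could be read as reassurance that reactogenicity does not depend on dose, when the test had little chance of showing that it does. The SAP already includes adjuvant beside dose in its longitudinal immunogenicity model (SAP 8.2), but does nothing similar for safety.

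**Working it through.** **The plan's own figures.** The documents state no power for this comparison. Safety sizing rests on exact confidence limits. With zero events the upper limit is 1 − 0.025^(1/n), which gives 20.6% (n = 16), 10.9% (n = 32) and 5.6% (n = 64). These match SAP Table 3.

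**Inputs.** From the documents: 16 per active group, so 32 vs 32 pooled and 16 vs 16 in each stage; two-sided 5%. Assumed, because no per-participant rates are given: 95% or 100% with ALFQ, and a range of rates without it. Protocol 5.5.1 offers only a per-injection anchor for IHV01 (196 of 241 injections without reactogenicity, placebo included). The exact binomial test is taken to be Fisher's.

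**Why pooling costs power.** Take 60% vs 20% without ALFQ and 95% in both doses with it.
- Arm rates are (0.60 + 0.95)/2 = 0.775 and (0.20 + 0.95)/2 = 0.575, a difference of 0.20.
- Pooled variance per person: 0.675 × 0.325 = 0.219. Approximate z = 0.20/√(0.219 × 2/32) = 1.71.
- Average within-stage variance: (0.40 × 0.60 + 0.95 × 0.05)/2 = 0.144. Approximate z = 0.20/√(0.144 × 2/32) = 2.11.

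The difference is the same; only the variance changes.

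**Exact calculation.** The pooled test treats the full-dose count as Hypergeometric(64, m, 32), given m events in total. The stratified exact test treats it as the sum of independent Hypergeometric(32, m₁, 16) and Hypergeometric(32, m₂, 16), given the events in each stage. Two-sided p is the total probability of outcomes no more likely than the one observed. Power sums the product of the four binomial probabilities over all tables with p ≤ 0.05.

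| Without ALFQ (full vs fractional) | With ALFQ (full vs fractional) | Pooled exact | Stratified exact |
|---|---|---|---|
| 60% vs 20% | 95% vs 95% | 26.4% | 44.8% |
| 70% vs 30% | 95% vs 95% | 32.4% | 43.6% |
| 90% vs 50% | 95% vs 95% | 44.3% | 49.7% |
| 40% vs 10% | 95% vs 95% | 7.7% | 29.2% |
| 60% vs 20% | 100% vs 100% | 27.2% | 50.5% |
| 60% vs 20% | 95% vs 80% | 55.3% | 67.7% |
| 60% vs 20% | 70% vs 35% | 83.1% | 83.1% |
| 50% vs 20% | 70% vs 40% | 62.1% | 62.4% |
| 40% vs 15% | 40% vs 15% | 53.1% | 51.5% |
| 30% vs 30% (size) | 95% vs 95% | 0.3% | 2.1% |

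The relative losses in the first four rows are 41%, 26%, 11% and 74% (for example, 1 − 26.4/44.8 = 41%). For the fallback tests in the first two rows, pooled chi-square gives 37.6% and 43.6%, against 58.0% and 57.0% for Cochran-Mantel-Haenszel.

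**One data set.** Suppose 10/16 vs 3/16 without ALFQ and 16/16 vs 16/16 with it. The pooled table is 26/32 vs 19/32, Fisher p = 0.099. The stratified exact p is 0.029. The conclusions at the SAP's 5% level are opposite.

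**The case against.** The strongest reply is one of scope. The near-universal rate is documented only for local pain and tenderness, and comes from trials of other antigens. Of the nine solicited rows in Table 15, six are Grade 2 or Grade 3 rows; the ceiling plausibly reaches only any local symptom and, through it, any solicited symptom. This stands. A reader might infer that the whole dose column is affected, but away from the ceiling the two tests are nearly equal, and with identical rates in both stages the pooled test is slightly ahead (53.1% vs 51.5%).

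A reader might also infer a fixed loss, say 25–45%. The documents do not support one: they give no rates, and the plausible sets tried run from about 5% to 85%.

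Nor is 5% the fair yardstick for conservatism. Exact tests of this size fall short of it anyway: the pooled test rejects about 2.4–3.3% when both stages share one rate of 30–80%. The like-for-like benchmark under the ceiling is the stratified exact test at 2.1%.

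A reader might suspect bias. Full and fractional dose are allocated 1:1 within each stage, so ALFQ is balanced across dose by design. The pooled test is valid and unconfounded; the issue is efficiency.

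Finally, the trial is described as exploratory and descriptive, Protocol 12.2.3 singles out ALFQ vs no ALFQ as its key safety comparison, and SAP Table 16 shows each group with its confidence interval. This lowers the stakes but does not close the gap. SAP 7.1.1 compares individual groups by interval overlap, and in the data set above the intervals (35–85% and 4–46%) overlap. At 60% vs 20% with 16 per group, the intervals separate only 20.9% of the time, against 50.5% power for Fisher's test in that stage alone.

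**Conclusion.** The point holds for the any-local and any-solicited rows. With about 95% affected under ALFQ at both doses, pooling reduces exact-test power from 45% to 26% (60% vs 20% without ALFQ), from 44% to 32% (70% vs 30%) or from 50% to 44% (90% vs 50%). With no dose effect and 30% without ALFQ, size is 0.3% against 2.1%. These figures assume 16 per cell, Fisher's test for the exact binomial test, and rates that the documents do not supply. A dose effect that also appears under ALFQ shrinks the loss (55% against 68% at 95% vs 80% with ALFQ).

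For systemic events, Grade 2+ events and other outcomes away from the ceiling, the documents give no reason to expect more than a small loss. Stratifying does not make the comparison well powered, since 45% still misses the effect more often than not. It removes an avoidable loss in the situation the protocol itself anticipates, at almost no cost elsewhere.

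**What to change.** In SAP 7.1.2 and the solicited rows of the dose column in Table 15, replace the pooled dose test with an exact conditional test stratified by ALFQ stage (Groups 1 vs 2, Groups 3 vs 4). Name Cochran-Mantel-Haenszel as the fallback in place of the unstratified chi-square. Beside the p-value, show the full-minus-fractional difference within each stage with its confidence interval, so that a ceiling under ALFQ is visible. Using the same test for unsolicited events in SAP 7.1.1 is optional, for consistency. The ALFQ vs no-ALFQ comparison is not affected by this point.

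The cost is a sentence or two in the SAP, a standard procedure option and extra columns in one table shell. No new data are needed.

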7.1.3. Clinical Laboratory Data

Clinical laboratory values, including change from baseline, will be summarized by vaccination group. The values will be graded according to the toxicity scale (see Protocol Appendix B) and, if clinically significant, reported as AEs.

Clinical labs will be presented by visit, grade, and vaccination group. Additionally, descriptive summary statistics (mean, SD, median, minimum, maximum) will be presented for each clinical lab, along with change from baseline summaries. If multiple baseline values are obtained, only the most recent value will be analyzed. For change-from-screening summaries, participants with an undefined change from screening, due to missing data, will be excluded.

Clinical laboratory values will be presented in listings as well.

8. IMMUNOGENICITY EVALUATION

8.1. Primary Immunogenicity Analysis

The primary immunogenicity endpoint is the magnitude of plasma IgG (antigen-specific) responses as measured by the endpoint titer, the same variable assessed in RV306. GMTs will be calculated for each group at each visit and the per-participant peak across all visits, along with 95% CIs (exponentiating the CI limits for the log GMT based on the normal distribution). Hypothesis testing is planned for targeted time points; this will be performed in order to aid in interpretation by helping to determine immune responses for potential further examination in future studies. First, group GMTs will be compared across all vaccination groups via ANOVA (null hypothesis that all groups share the same GMT) at the 5%-level, and if that is found to be significant, pairwise comparisons via 2-sided t-tests and the Bonferroni-Holm step-down procedure will be made and a 1% significance threshold will be applied. The two collapsed comparisons will be via 2-sided t-tests of log-GMTs at the $\alpha=0.025$ -level. If the data appear especially non-normal, nonparametric testing will be considered instead.

The reverse cumulative distribution (RCD) of titers (with endpoint titer on the x-axis and the proportion of participants with at least that titer on the y-axis) at each visit will be shown by vaccination group, separately for each antigen.

Seroconversion or seropositivity post-vaccination will be defined based on criteria given by the performing lab, and the number and percent of participants in each group achieving seroconversion/seropositivity at each visit will be presented along with the associated exact 95% Clopper-Pearson CI. The same group comparisons will be performed, via exact binomial tests and the same handling of significance and multiplicity.

Immune response over time (durability) will be assessed by the positive incremental area under the curve (AUC) based on a graph with log endpoint titer on the y-axis and visit day on the x-axis. For comparability between participants with different numbers of samples (visits) available, these values will be scaled by the week of the last available sample. If no sample is available for visits other than the first and last, no explicit imputation will be done, and the AUC will be calculated based on available samples. Log AUC will be analyzed similarly to the visit-by-visit titers.

The week of peak response will also be described by vaccination group, with no hypothesis testing planned. If, by chance, there are equivalent peak responses at two visits, the first will be considered the peak.

